5.1 PARTICIPANT COMPENSATION

Participants will be compensated up to \$330-525 for completed activities. Completion of menstrual cycle 1 will be compensated as \$35. In the menstrual cycle 2, participants will be compensated \$15 for visits 1-5 and \$20 for visits 6-8 completed during cycle 2. Participants who did not reach LH peak in cycle 2 will return to complete additional visits in cycle 3 and will be compensated \$25 for blood draw visits 1-5 and \$30 for blood draw visits 6-8. Participants will be compensated \$20 only if computerized tasks of cognition are completed on both blood draw visit 2 or blood draw visit occurring on same day as peak LH and blood draw visits 7 or 8. Participants will be compensated with \$140 for completion of the Trier Social Stress Test. Depending on immigration status in the United States and UIC employment status, participants will receive compensation as a combination of cash and a check in the mail, as a combination of cash and through the payroll system, only as a check in the mail, or only through payroll system.

See Table 1 for details.

Compensation for Study Part	Permanent resident or a US citizen (UIC Employees)		Permanent resident or a US citizen (non-UIC Employees)		Nonresident alien eligible to receive payment*	
	Amount	Timeline	Amount	Timeline	Amount	Timeline
Menstrual Cycle 1	\$35 in cash	\$35 on visit 1 of Menstrual Cycle 2	\$35 in cash	\$35 on visit 1 of Menstrual Cycle 2	\$35 as a check	Check within 4 to 6 weeks
Menstrual Cycle 2 **	\$15 per visit for visit 1-5 \$20 for visit 6-8 \$140 for completion of	\$100 in cash on visit 8. Payroll within 4 to 6 weeks	\$15 per visit for visit 1-5 \$20 for visit 6-8 \$140 for completion of	\$100 in cash on visit 8. Check within 6 to 8 weeks	\$15 per visit for visit 1-5 \$20 for visit 6-8 \$140 for completion of	Check within 6 to 8 weeks

[figure not shown]
	the 4-hour task session.		the 4-hour task session.		the 4-hour task session.	
Menstrual Cycle 3) ***	\$25 per visit for visit 1-5 \$30 per visit for visit 6-8	Payroll within 4 to 6 weeks	\$25 per visit for visit 1-5 \$30 per visit for visit 6-8	Check within 6 to 8 weeks	\$25 per visit for visit 1-5 \$30 per visit for visit 6-8	Check within 6 to 8 weeks

6.0 STUDY DESIGN AND PROCEDURES

This study will be conducted only at the University of Illinois. Study spaces will be rented at the Center for Clinical and Translational Science. Research staff working out of the PI’s laboratory will ensure regulatory compliance, recruit participants, and collect and analyze data. The PI’s lab is located on the first floor of UIC College of Pharmacy. Study materials, equipment, and all paper documentation will be locked in the office of research staff affiliated with the study. This is a cohort design study. Participants’ data will be shared in a de-identified manner with a National Institute of Health (NIH) NIMH data repository.

6.1 PROCEDURES AND ASSESSMENTS

Procedures and assessments occurring in each study phase is outlined in figure 2.

[figure not shown]
6.1A. SCREENING

Following the completion of the online survey, study participants will be scheduled for an in-person screening interview, at which time all the criteria listed in sections 4.1 and 4.2 will be assessed. Participants will also be instructed to complete a Demographics Survey during the screening. The purpose of the Demographics Survey is to compare the makeup of each experimental group and ensure that there is no significant demographic difference in the composition of the PMS/PMDD case vs. control group.

6.1B. MENSTRUAL CYCLE 1

The purpose of menstrual cycle 1 and 2 are to establish Premenstrual Syndrome diagnosis, Premenstrual Dysphoric Disorder diagnosis, or the healthy control status. Every day, participants will be asked to complete

the Daily Record of Severity of Problems (DRSP) (Endicott et al., 2006) in which they will chart their menstruation timing as well as give a score of 1 to 6 for affective or somatic symptoms according to their severity. Study physician, [name] (Assistant Clinical Professor of Psychiatry/Director of Addiction Psychiatry at UIC) will review DRSPs and provide Premenstrual Syndrome diagnosis when mean score 5 days before menstruation exceeds 50, mean luteal phase score is at least 30% higher than that of the follicular phase, and at least 3 symptoms score more than 3 in the 2-month period (see Deng et al., 2018, supplement). Otherwise, study participants will be classified as healthy controls. [name] role on the project is to provide the PMS or PMDD diagnosis as well as help with the recruitment of study participants. In addition, the study physician will be responsible for suicidality risk assessment (see Section 8.0).

6.1C. MENSTRUAL CYCLE 2

Table 2. Original Schedule of Study Visits According to Average Cycle Length

Average cycle length (days)	Visit 1 Menses	Visit 2 Mid follicular	Visit 3 Perioovulatory 1	Visit 4 Perioovulatory 2 ^a	Visit 5 Perioovulatory 3	Visit 6 Early luteal	Visit 7 Mid luteal	Visit 8 Late luteal
21	2	4	5	6	7	11	15	20
22	2	4	6	7	8	12	16	21
23	2	5	7	8	9	13	17	22
24	2	5	8	9	10	14	18	23
25	2	6	9	10	11	15	19	24
26	2	6	10	11	12	16	20	25
27	2	7	11	12	13	17	21	26
28	2	7	12	13	14	18	22	27
29	2	7	13	14	15	19	23	28
30	2	8	14	15	16	20	24	29
31	2	8	15	16	17	21	25	30
32	2	9	16	17	18	22	26	31
33	2	9	17	18	19	23	27	32
34	2	10	18	19	20	24	28	33
35	2	10	19	20	21	25	29	34

In the menstrual cycle 2 (Figure 3), study participants will continue daily DRSP completion. Study participants will use the Clearblue Connected smartphone application (free to download) during menstrual cycle 2 which

records results from daily Clearblue Connected Ovulation Test System urine tests in order to capture LH surge. A participant will start the testing according to the manufacturer's instructions. Only one sample (i.e. the first daily urine sample) is tested per day before 7:00 AM. Participants will take a photo of the result and upload it to REDCap, to measure adherence.

Based on the average menstrual cycle length from cycle 1, participants will be provided with a blood draw schedule outlined in Table 2 on their first day of menses, though blood draw visits 3, 4, and 5 may change depending on the results of the ovulation test. If the ovulation monitor indicates "peak" fertility outside of blood draw visits 3, 4, or 5, study participants will be required to come to the CCTS the same day and the subsequent 2 days. For example, a participant with 32 day-cycle is tentatively scheduled for blood draws on 16th, 17th, and 18th of the month. However, if the monitor indicates LH peak on the 14th, the participant will need to undergo blood draw on the 14th, 15th and 16th. ELISA analysis of LH hormones requires fasted blood samples, so participants will be informed that they must plan to fast for the morning of each blood draw session, with the possibility of having to fast for one unscheduled visit. If a participant does not reach an LH peak by blood draw visit 7 during cycle 2, blood draw visit 8 will be canceled. The participant will be required to complete blood visits 1-8 during the subsequent month, cycle 3. If a participant does not reach an LH peak by blood draw visit 7 during cycle 3, the participant will be ineligible to complete remaining visits or remain in the study. The In-Person Blood Draw sessions are broken down into two parts. The first part of the session will begin at 8:00am during 6 visits at CCTS (the remaining 2 visits are described below). Participants will be asked to rinse their mouth thoroughly with water and wait for 10 minutes. During this time, the heart rate monitor will be placed for the purpose of measurement of heart rate variability. The measurement will take 5 minutes. After the heart rate monitor is removed, participants will complete a sleep diary. Next, a saliva will be collected via passive drool. Participants may tilt the head forward, allowing the saliva to pool on the floor of the mouth, then pass the saliva through the SalivaBio Collection Aid (SCA) into a polypropylene vial. After this, a needle will be placed in participants' arm and they will be asked to remain still while their blood is drawn. The study session will end at 8:30am.

In addition, participants will be randomly assigned to perform the second part of the session on both blood draw visit 2 or blood draw visit occurring on same day as peak LH and blood draw visit 7 or blood draw visit 8. Peak LH visit will be the day of peak fertility of participants. The study session will begin at 8:00am. Participants will be asked to rinse their mouth thoroughly with water and wait for 10 minutes. During this time, the heart rate monitor will be placed to measure heart rates for 5 minutes. Then, participants will be asked to provide saliva samples. Following this, study participants will take three computerized tests of cognition, measuring working memory, response inhibition and attention. The tests will be administered using Psytoolkit (<https://www.psytoolkit.org/>), an online platform for running psychology experiments. The duration of the tests is 15 minutes. Next, blood draws will occur from 8:35-8:45. The session will end at 8:50am.

6.1d. Trier Social Stress Test

During the second or third menstrual cycle (depending on whether an LH peak occurs in the second menstrual cycle), study participants will also attend a procedure designed to test their stress reactivity (Figure 4). The stress procedure will be scheduled in between blood draw visits #7 and #8 (See Table 2). Laboratory study session will begin at 11:00 at CCTS. First, a urine drug screen will be collected for the purpose of ruling out drug intake, along with CO testing for the purpose of ensuring absence of smoking. Around 11:15, participants will be offered a choice of snack – a granola bar or crackers. An intravenous catheter will be placed at 11:30. Participants will enter the relaxation phase from 11:30 to 13:00, during which they will read neutral materials or watch a neutral

movie. The relaxation phase is necessary for any stress encountered as the result of catheter insertion to subside.

The Trier Social Stress Test (Kirschbaum et al., 1993) will begin at 13:30 in order to minimize circadian variations in cortisol levels. Participants will be given verbal instructions for the TSST speech and mental arithmetic performance tasks. The document “TSST.Instructions.doc” is attached. Participants will be told that they will be taking on the role of an applicant for their ideal position and that they must deliver a 5-min speech which will convince a panel of interviewers that they are the best candidate for a self-identified ideal job. They will also be told that they will be performing another task, which will be given by the panel. Please note, per consent form, that participants already consented to give a public speech as part of the study.

Study participants will be given 10 minutes to prepare for the task, and then escorted to another room, with three interviewers in white coats sitting at a table. The interviewers will follow a strict protocol by exhibiting unemotional neutrality and avoiding any oral or mimic feedback. Participants will be instructed to step in front of a microphone, which permits the study subjects to have a clear view of the panel. Participants will be expected to utilize the entire 5 minutes for the speech and will be prompted as needed by the interviewers. For the second 5-minute task, participants will be asked to subtract 13 from 1,022 as fast as possible and speak their answer aloud. They will be asked to start again if they made a mistake. After the tasks, participants will be escorted back to the study room for the collection of various samples as shown in Figure 4 through 14:50. The discharge procedure will include removal of the intravenous line, completion of adverse event form and debriefing. The study procedure will end at 15:00.

6.2 SPECIMEN CONSIDERATIONS

6.2.1 URINE SPECIMEN (IN-PERSON SCREENING)

Urine drug specimens will be collected from participants during In-Person Screening. The purpose of the specimen is two-fold: 1. urine drug screen and 2. pregnancy test. Specimens will be collected and tested at the UIC College of Pharmacy. The label will include the information that will be on the urine collection cup during urine drug screen and urine pregnancy testing. Research staff will document test results on the study flowsheet.

For the drug screening, research specialist will verify the temperature strip on the collection cup is between 90 – 100°F within 4 minutes of urine collection. The research specialist will read drug of abuse test results by pulling label from right to left to remove expose test results in 5 minutes. For pregnancy testing, the research specialist will use Serum/Urine hCG-STAT chromatographic immunoassay by transferring 3 full drops of urine to the specimen well of the test device. The result will be read at 3 to 4 minutes when testing a urine specimen.

6.2.2 MENSTRUAL CYCLE 2 (SPECIMEN COLLECTION ACROSS THE MENSTRUAL CYCLE)

Participants will collect first morning urine specimens during menstrual cycle 2. Urine specimens will be used for daily hormone testing with the Clearblue Connected Ovulation Test System. Participants will dispose of their specimen in the sink or toilet upon completion of daily testing. Specimens will not be stored.

Blood and saliva specimens will be collected by research staff from participants during in-person blood draw visits (totaling 8 visits across the menstrual cycle) as outlined in Table 3. Research staff will extract plasma and peripheral blood mononuclear cells (PBMCs) from whole blood. Neuroactive steroid biosynthesis will be determined by levels in the plasma using gas chromatography-mass spectrometry and real time PCR (qPCR) for measuring the mRNA levels of key enzymes involved in the neuroactive steroid biosynthetic pathway.

Collection tube (no. tubes x volume)	Specimen type	Volume to be drawn	No. aliquots x volume	Analytes	Test Lab	Storage Location
Red top Serum Separation tube (2 x 6.0 mL)	Serum	9 mL	1 x 0.6 mL	LH/FSH/Estradiol	ARUP	[name] Lab
			1 x 0.4 mL	Progesterone	UIC RRC	[name] Lab
			1 x 0.5 mL	Allopregnanalone	UIC RRC	[name] Lab
			2 x 0.5 mL	Extra stored	UIC RRC	[name] Lab
			N/A	Plasma	UIC RRC	[name] Lab
Purple top EDTA tube (1 x 6.0 mL)	Whole blood	6 mL	1 x 6 mL	Peripheral blood mononuclear cells	UIC RRC	UIC RRC
Salimetrics Collection Tube	Saliva	1.5 mL	1 x 0.5 mL	Cortisol	Salimetrics	[name] Lab

6.2.3 MENSTRUAL CYCLE 2 (ACUTE STRESS PROCEDURE)

Blood and saliva specimens will be collected by research staff from participants during the Trier Social Stress Session as outlined in Table 4.

Collection tube (no. tubes x volume)	Specimen type	Volume to be drawn (per one blood draw*)	No. aliquots x volume	Analytes	Test Lab	Storage Location
Red top Serum Separation tube (1 x 5.0 mL)	Serum	5 mL	1 x 0.5 mL	Extra stored	UIC RRC	[name] Lab
			1 x 0.5 mL	Allopregnanalone	UIC RRC	[name] Lab
			N/A	Plasma	UIC RRC	[name] Lab
Salimetrics Collection Tube	Saliva	1.5 mL	1 x 0.5 mL	Cortisol	Salimetrics	[name] Lab

*There are total 7 blood draws and saliva collections during the Trier Social Stress Test session

6.3 PROSPECTIVE DATA

Participants will report symptoms of PMS online through REDCap (DRSP). The DRSP refers to symptoms experienced in the past day and will be conducted every evening during 2 menstrual cycles (We anticipate that approximately 5-10% of study participants will not ovulate in the 2nd menstrual cycle, and will need to enter the 3rd menstrual cycle. In this case, participants who enter the third menstrual cycle will complete DRSPs.). Data will not be collected retrospectively.

REDCap will only be accessed by the PI and her research team on password protected computers in the PI's lab located on the first floor of UIC College of Pharmacy. This research project will be shared amongst the research team in REDCap and each member will be able to access the information by logging into the REDCap database under their individual profiles. Participants' personal information will be stored in REDCap to ensure

protection of personal identifiers. Software needed to collect study data from research devices during testing sessions will be downloaded on PI’s research laptop. As discussed, the PI’s laptop is password-protected and only available to members of the research team. No identifiers will be stored on the laptops. Hard copy files will be stored in locked cabinets inside the locked offices in the PI’s lab located in the UIC College of Pharmacy - [name]. The PI’s lab consists of two rooms within UIC College of Pharmacy – room 117A and 115. The Principal Investigator and her designated research team will have access to the research study information.

7.0 EXPECTED RISKS/BENEFITS

There are no expected benefits to the participants of this research study, however, it is expected that a better understanding of hormone kinetics and stress will lead to a more sophisticated understanding of Premenstrual Syndrome. We do not anticipate any risks of particular severity or seriousness.

There is a risk of distress from answering personal questions about participants’ mental health history during the Mental Health Interview. Saliva collection via passive drool may be uncomfortable for participants. Blood draw side effects include discomfort, bruising and/or bleeding at the needle site (>20%); dizziness and infection (<2%). These side effects are generally benign and reversible. Also, study subjects may feel discomfort and distress from Trier Social Stress Test.

Additionally, there is a potential risk of loss of confidentiality. Information that identifies subjects will only be shared between research staff involved in this particular study. The research team will make every effort to protect subject’s private health information and guard against any loss of privacy. Participant information will be securely stored and only accessible to authorized personnel as described in section 8.0 “Data Collection and Management Procedures”.

There is a potential risk of discomfort or awkwardness associated with at-home urine testing with the Clearblue Connected Ovulation Test System. Additionally, there is a risk of discomfort or stress from revelations and concerns regarding failed ovulation detection or infertility.

8.0 DATA COLLECTION AND MANAGEMENT PROCEDURES

Data collection will occur throughout the 2-menstrual cycle study procedure. Table 5 outlines each of the data collection tools along with information when in the study they are collected.

Table 5. Questionnaires and physical measurements by visit type

Data Collection Tool	PRE-SCREENING	SCREENING	Menstrual Cycles 1 and 2 (DAILY)	Menstrual Cycle 2 VISIT 1	Menstrual Cycle 2 VISIT 2	Menstrual Cycle 2 VISIT 3	Menstrual Cycle 2 VISIT 4	Menstrual Cycle 2 VISIT 5	Menstrual Cycle 2 VISIT 6	Menstrual Cycle 2 VISIT 7	Menstrual Cycle 2 VISIT 8	ACUTE STRESS REACTIVITY STUDY
Initial Survey	✓											
Medication and Health Review		✓										
Shipley IQ Test		✓										
Mental Health Interview		✓										
Demographics Survey		✓										
Substance Use Survey		✓										
Physical Activity		✓										
State-Trait Anxiety Inventory (Y-2 only)		✓										
Beck’s Depression Inventory		✓										
Personality		✓										
Physical Measures*		✓										
Daily Record of Severity of Problems			✓									
Adverse Event Questionnaire				✓	✓	✓	✓	✓	✓	✓	✓	✓
Adverse Event Tracking Form				✓	✓	✓	✓	✓	✓	✓	✓	✓

Task Perception Rating												✓
Heart Rate			✓	✓	✓	✓	✓	✓	✓	✓	✓	✓
Computerized Cognition Tasks				✓	✓					✓	✓	
Visual Analogue Scale												✓
Blood Pressure												✓
Sleep Diary			✓	✓	✓	✓	✓	✓	✓	✓	✓	✓

*Includes: height; weight; blood pressure; pulse; sitting knee and abdominal height; waist, hip, abdominal, arm and thigh circumference.

Responses from Demographics, Physical Activity, Strait-Trait Anxiety Inventory (Y-2), Becks Depression Inventory, Personality, Physical Measurement, DRSPs, Task Perception Rating, VAS, Blood Pressure, Date of blood draws, Date of day 1 of cycle, and Date of ovulation surveys will be de-identified and submitted to NIH NIMH data repository. The repository will only be accessed by the PI and an assigned research staff on password protected computers.

The Mental Health Interview will be administered verbally and includes a question about suicide risk. This question is a not part of an evaluation of suicide risk per se. Study coordinator will call [name] regarding any person reporting that he/she is suicidal (as part of Depression assessment). [name] will conduct an assessment by asking further questions related to suicidality using the attached MINI-International Neuropsychiatric Interview. Individuals scoring “low suicidality” and without imminent threat will be given referral to UIC Adult Psychiatry Service [contact]). [name] will contact [name] for an in-person assessment for individuals with moderate/high suicidality. For those exhibiting an immediate danger, authorities may be called if [name] or [name] view it necessary.

Participants who consent to the study by signing the ICD will be assigned a unique Subject ID, consisting of 7 numbers. Screening flowsheets will be labeled with Subject ID only. Only the consent, which will be locked in the PI’s laboratory will have study participant’s identifier (name and signature). All paper copies – with and without identifiers - will be stored in the PI’s UIC lab located on the first floor of the UIC College of Pharmacy.

Participants will perform computerized tasks from the PsyToolkit website. Only subject ID will be entered and task performance results will be downloaded from the website. The Clearblue Connected application may collect personal information about users including name, age, gender, birth date, health-related information, email address, fertility information, social media account names, authentication information, inventory of other installed information, cookies (application use), and microphone and camera data. The Clearblue Connected application uses industry standards (security and vulnerability scans, software audits, firewalls, data encryption) to protect user privacy, and will not willfully share user information without user consent. Participants are informed of the Clearblue Connected application’s security features in the Informed Consent Document. The research team will not download any personal data from the application and will only collect relevant information about hormone changes from the application.

REDCap will only be accessed by the PI and her research team on password protected computers in the PI’s lab located on the first floor of UIC College of Pharmacy. This research project will be shared amongst the research team in REDCap and each member will be able to access the information by logging into the REDCap database under their individual profiles. Participants’ personal information will be stored in REDCap to ensure protection of personal identifiers. As discussed, the PI’s laptop is password-protected and only available to members of the research team. No identifiers will be stored on the laptops. Hard copy files will be stored in locked cabinets inside the locked offices in the PI’s lab located in the UIC College of Pharmacy - [name]. The PI’s lab consists of two rooms within UIC College of Pharmacy – room 117A and 115. The Principal Investigator and her designated research team will have access to the research study information. There will be no collaborators involved in this study.

9.0 DATA ANALYSIS

The study will recruit approximately 1500 participants over a 4-year period. This recruitment number accommodates screen failures, with the total number of participants completing the study at 120.

The primary evaluation is a repeated measure analysis, testing for differences in study outcomes by PMS/PMDD diagnosis. General Estimating Equations will be implemented to analyze all repeated measures. Time will be modeled as a categorical, dummy variable in order to avoid an *a priori* shape assumption, as is otherwise encountered with the use of a mathematical function to model development over time (Twisk, 2013). As shown in a GEE model in a study involving administration of TSST (Xin et al., 2017), every subsequent measurement (coded as a dummy variable) after the baseline measurement is used as a time indicator. An interaction between group (with vs. without PMS/PMDD diagnosis) and categorical (dummy) time variable will be added to the model in order to detect a difference in study outcomes over time between the two groups.

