12.0 STATISTICAL CONSIDERATIONS

Power Calculation: The primary hypothesis is that study participants with the PMS/PMDD diagnosis will have a blunted acute stress cortisol response compared to participants without the diagnosis. Means and standard deviation from Table 2 of Huang et al. (2015) were entered into GLIMMPSE for all the time points. Base correlation was estimated as 0.7, with decay rate as 0.2. Means were scaled as 0.8, 1 and 1.2. Alternative values for variability were derived by scaling the calculated covariance matrix by 0.5, 1, and 2. Results are presented in Figure 5. With 90% power, alpha level set at 0.05 variability scale factor of 2 and mean scale factor of 1.2, 120 study participants in total are needed to detect a time by group interaction.

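### Section 9 leaves the GEE interaction test unspecified; the usual joint Wald test with an uncorrected sandwich variance would run at about 7.5%, not 5%, with 120 women in equal groups

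*Combined protocol and SAP*

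**What the plan says.** Section 9.0 sets the method for every longitudinal outcome: "General Estimating Equations will be implemented to analyze all repeated measures". Time is categorical, and following a cited stress-test analysis "every subsequent measurement (coded as a dummy variable) after the baseline measurement is used as a time indicator". The comparison of interest enters as follows: "An interaction between group (with vs. without PMS/PMDD diagnosis) and categorical (dummy) time variable will be added to the model". The section plans recruitment "with the total number of participants completing the study at 120".

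Section 12.0 names the primary hypothesis, a blunted cortisol response to acute stress in women with the diagnosis. It gives the design figures as "With 90% power, alpha level set at 0.05 variability scale factor of 2 and mean scale factor of 1.2", concluding that "120 study participants in total are needed to detect a time by group interaction". The note to the specimen table in Section 6.2.3 fixes the number of repeated measures: "There are total 7 blood draws and saliva collections during the Trier Social Stress Test session".

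The documents do not state the variance estimator (robust or model-based), the working correlation, the test (Wald or score), its reference distribution, any small-sample correction, or a case:control ratio.

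**The concern.** Seven samples with baseline as reference give six interaction coefficients. GEE is most often run with the empirical (sandwich) covariance and a Wald statistic referred to chi-square. That covariance is biased downward in finite samples, and the chi-square reference treats it as known. Both errors are small for one coefficient. They add up when six are tested jointly with about 120 clusters, and they grow when one group is small, because the smaller group's covariance is estimated from few women.

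At stake is the p-value for the primary hypothesis. If the analyst accepts common software settings, the test will reject a true null more often than the 5% in Section 12.0. If the choice is left until the data are in hand, the primary test also acquires an avoidable post hoc decision.

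**Working it through.** **The plan's own figure.** The total of 120 at 90% power cannot be recomputed, because the means and standard deviations come from a cited table that is not in the documents. The check therefore concerns only the type I error of the test.

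**Inputs.** Alpha 0.05 and N = 120 (Sections 12.0 and 9.0). Seven samples (Section 6.2.3), so q = 7 − 1 = 6. Eight hormone visits (Section 3.0), so q = 8 − 1 = 7. Assumptions: complete, normal data; equal covariance in both groups unless stated otherwise; splits of 60:60, 48:72 and 36:84. The 36:84 split is 30% of 120, borrowing the population prevalence in Section 1.0.

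**Form of the test.** With complete data and a saturated group-by-time model, the GEE interaction estimates are differences d between groups in mean change from baseline. The uncorrected sandwich covariance is

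V = SS₁/n₁² + SS₂/n₂²,

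where SS is the within-group sum of squares and products of the changes. The Wald statistic is W = d′V⁻¹d, referred to chi-square(6), with critical value 12.59. Under these assumptions its size does not depend on the correlation.

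**Equal groups (exact).** With n per group, W = T² × 2n/(2n − 2), where T² is Hotelling's statistic. For n = 60:

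- T² at the cut-off = 12.59 × 118/120 = 12.38
- F = 12.38 × 113/(118 × 6) = 1.976
- P(F(6,113) > 1.976) = 7.5%

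The same steps with q = 7 give 8.0%. If fewer women provide stress data (an assumption), the exact 6-df figure is 8.1% at 50:50 and 9.0% at 40:40.

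**Unequal groups and other tests.** Simulated size at N = 120 and 6 df, 60,000 null trials per cell, Monte Carlo error about 0.1 point:

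| Test | 60:60 | 48:72 | 36:84 |
|---|---|---|---|
| Uncorrected sandwich, chi-square(6) | 7.7% (exact 7.5%) | 7.8% | 9.5% |
| Uncorrected sandwich, F(6,118) | 6.6% | 6.8% | 8.4% |
| Mancl-DeRouen sandwich, chi-square(6) | 6.6% | 6.8% | 8.1% |
| Generalized score test | 4.8% | 4.6% | 4.3% |
| Pooled-covariance Hotelling F | 5.0% | 5.0% | 5.0% |

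Repeat simulation put 48:72 at 7.9% and 36:84 at 9.4% to 9.7%. GEE software with an exchangeable working correlation gave 8.1% and 8.7% at 60:60 and 36:84 in 1,500 runs (standard error about 0.7 point), and 6.5% and 9.6% in about 2,800 runs. Both are compatible with the table. A lognormal outcome reduces the inflation to 7.0% and 8.2%.

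**Single coefficients.** One interaction coefficient tested alone has size of about 5.3% at 60:60 and 5.8% at 36:84, which corresponds to interval coverage of about 94.7% and 94.2%.

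**Candidate remedies.** A Mancl-DeRouen sandwich with the ordinary F(6,118) still gives 5.7% to 7.1%. With the Hotelling scaling, W × 113/(118 × 6) is referred to F(6,113), whose 5% point is 2.180. At 60:60 the corrected W equals T² × 59/60, so the size is P(F(6,113) > 2.180 × 60/59 = 2.217) = 4.6%. At 36:84 it is about 6%. When case variance was half or double that of controls at 36:84, the pooled-covariance test gave 1.3% or 13.7%. The Mancl-DeRouen version with Hotelling-scaled F stayed between 4.7% and 6.7% in the 6-df settings run.

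**The case against.** The strongest reply is that the faulted test is not in the plan. Section 9.0 says GEE and no more, and a generalized score test is also GEE and holds its level. That stands. A reader might infer that the plan prescribes an invalid test, but the documents support only that it leaves the choice open and that the commonest choice misses 5%.

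The joint test is also inferred. Section 12.0 speaks of detecting a time-by-group interaction, which favours a joint test without naming one. If coefficients were read one at a time, the sandwich distortion would be minor.

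Three stronger readings should be resisted:

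- **That the error is 9% to 10%.** This needs a split near 30:70. Groups are formed by diagnosis (Section 6.1B) and no ratio is stated, so imbalance is possible. But Section 5.0 describes targeted recruitment of women with PMDD, which would raise the share of cases.
- **That the confidence intervals are materially too narrow.** The single-coefficient results show otherwise.
- **That the planned test differs from the one powered.** Section 12.0 names the power software but not the test chosen in it, so the documents cannot settle this.

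**Conclusion.** The concern holds as a gap with a measurable consequence. Run in the usual way, the primary 6-df interaction test has a true type I error of about 7.5% with 60 women per group, about one and a half times the nominal level (7.5/5 = 1.5). The equal-group figure is exact for complete normal data with equal covariances. The figures of about 7.9% at 48:72 and 9.5% at 36:84 are conditional on splits that the plan does not state. The hormone analyses share the problem at 7 df. The harm is to the joint p-value, not to the estimates or, materially, to their individual intervals. The point deserves correction before analysis because it bears on the primary hypothesis and is cheap to close.

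**What to change.** Keep the GEE mean model and add to Section 9.0 that the group-by-time interaction is tested jointly by one of these:

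- **Corrected sandwich with scaled F.** Mancl-DeRouen covariance, with W × (N − 1 − q)/((N − 2) × q) referred to F(q, N − 1 − q), where N is the number of women analysed. For 6 df and N = 120 this is W × 113/(118 × 6) against F(6,113). For the hormone models it is W × 112/(118 × 7) against F(7,112). The scaling must be written out, because a corrected sandwich with an unspecified F reference does not restore 5%.
- **The GEE generalized score test**, referred to chi-square(q).

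A repeated-measures linear model with unstructured covariance and a Kenward-Roger F test is an alternative. If the groups are unequal, its covariance should be allowed to differ by group, since a pooled covariance can miss 5% badly when variances differ.

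State the working correlation in the same sentence. The cost is that sentence, a software option or a few lines of code, and slightly larger p-values. The corrected sandwich would still run at about 6% at a 30:70 split, and the score test is somewhat conservative there (4.3%).
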